9.3.1 Analysis of the Primary Endpoints

The incidence of clinically confirmed recurrence of the primary hernia occurred to date, including not previously reported in T-GENVIH-002 study will be summarized. The proportion of subjects with the incidents will be presented.

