3.1 Primary Objective

The primary objective of this study is to capture existing clinical performance data to confirm the continued performance of the Gentrix® Surgical Matrix as a long term follow up (LTFU) to T-GENVIH-002 study for minimally invasive surgical approach (laparoscopic and robotic) sub-population of cases post primary hernia surgical repair to date, not previously reported in the T-GENVIH-002 study.

Existing clinical data support the safety and performance of the Gentrix® Surgical Matrix. There are currently no safety concerns with these products. This clinical investigation will confirm the safety and performance of the Gentrix® Surgical Matrix particularly in MIS cases and identify any unknown or not previously reported side-effects.

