10.4.3 Analysis of the Primary Endpoint(s)

The primary endpoint for this study is descriptive statistics of clinically confirmed recurrence of the primary hernia to date, including not previously reported in T-GENVIH-002 study.

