3. STUDY OBJECTIVES

The primary objective of this study is to collect additional safety data and demonstrate the performance of Integra GENTRIX® Surgical Matrix for reinforcement of ventral hernia repairs from a sub-population of participants in the T-GENVIH-002 study, specifically those with laparoscopic or robotic repair. Prospective data will be collected and assessed for later post-operative surgical site events and complications in the post-operative period from the last timepoint of data collection in T-GENVIH-002 to present. The safety objective of this study is to capture existing GENTRIX® Surgical Matrix Complication data in the longer term period post primary repair procedure, not previously reported in T-GENVIH-002 study. This study adds to the available data evaluating the safety and effectiveness of GENTRIX® Surgical Matrix in ventral hernia repair, particularly in a real-world population and particularly in the sub-population of minimally invasive surgery (MIS) cases (i.e., laparoscopic and robotic) from the GENVIH-002 study.

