7. ANALYSIS POPULATION

Enrolled: The enrolled population includes all eligible subjects based on the defined inclusion and exclusion criteria.

Intent-to-Treat (ITT) Population: All subjects who are enrolled into the study provide informed consent waiver and receive study intervention.

Per-Protocol (PP) Population: All subjects in the full Analysis Set not identified as major protocol violations.

The endpoints analysis will be based on the Intent-To-Treat population. The per-protocol set will be supportive and will be used to assess the robustness of study results if necessary. Safety analysis will be based on the Intent-To-Treat population.

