9.3 Endpoint Analysis

Primary, Secondary and Safety Endpoints will be analyzed based on the Visit 1 Questionnaire report.

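### The primary analysis gives one recurrence proportion and no estimate of new recurrences after T-GENVIH-002, and the documents conflict on which events that proportion counts

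*SAP*

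**What the plan says.** **Objective.** Protocol 3.1 aims to confirm continued performance in the laparoscopic and robotic "sub-population of cases post primary hernia surgical repair to date, not previously reported in the T-GENVIH-002 study". SAP 3 describes assessing later events in the period "from the last timepoint of data collection in T-GENVIH-002 to present".

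**Endpoint and analysis.** Protocol 10.4.3 asks for descriptive statistics of "clinically confirmed recurrence of the primary hernia to date, including not previously reported in T-GENVIH-002 study". SAP 9.3.1 turns this into a single summary: "The incidence of clinically confirmed recurrence of the primary hernia occurred to date, including not previously reported in T-GENVIH-002 study will be summarized", followed by "The proportion of subjects with the incidents will be presented". SAP 9.3.1 names no denominator. SAP 7 supplies one: "The endpoints analysis will be based on the Intent-To-Treat population". No at-risk set is defined.

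**Source and window.** SAP 9.3 states: "Primary, Secondary and Safety Endpoints will be analyzed based on the Visit 1 Questionnaire report". Protocol 6.1.2 starts that questionnaire at the last T-GENVIH-002 data collection. The Protocol synopsis (study visits row) and SAP 5 instead start data collection on the day of the index repair.

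**The concern.** A long-term follow-up of an earlier study should show whether repairs that were intact when that study ended have stayed intact. The plan specifies one percentage, and its wording suggests that recurrences already reported in T-GENVIH-002 are counted together with later ones. The same percentage could then mean that every failure was early and none is new, or that every failure is new. No specified summary gives new recurrences among subjects still recurrence-free at their last T-GENVIH-002 contact.

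If the percentage is instead meant to hold only new events, its label is wrong, and subjects who had already recurred remain in the denominator although they can no longer have a first recurrence. Either way, a report could describe continued performance from a figure that does not isolate the later period.

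**Working it through.** **Step 1. Which events enter the numerator?**

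*For a cumulative count:*
- The endpoint runs to date and treats unreported events as a part of what is counted (Protocol 3.3 and 10.4.3; SAP 3.1 and 9.3.1).
- The Protocol synopsis and SAP 5 collect from the day of surgery.
- The safety endpoint (SAP 3.3) and SSOPI (Protocol 3.4, SAP 3.2 and 9.2.6) are limited to unreported events, without the word "including" that the primary endpoint carries, so the difference looks deliberate. This is not conclusive: SSOPI does carry that word in the synopsis and in Protocol 10.1 and 10.4.4.

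*For new events only:*
- SAP 9.3 takes the endpoint from the Visit 1 questionnaire, and Protocol 6.1.2 starts that questionnaire at the last T-GENVIH-002 collection.

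The cumulative reading has more support, but the text does not settle it.

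**Step 2. Does another planned output give the new-event estimate?**

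The Kaplan-Meier curve in SAP 9.2.8 is worded for subjects with recurrences only and has no landmark at the end of T-GENVIH-002. SAP 9.2.6 adds by-subject listings, from which a split might be derived but is not specified.

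**Step 3. How far can the figures differ?**

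There is no plan figure to reproduce: SAP 8 says the sample size is not based on hypothesis testing, and no rate or precision target is given.

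Inputs:
- N = 21, the approximate planned size (Protocol 10.2, SAP 8), assuming all enrol and answer.
- k = recurrences known from T-GENVIH-002, and m = new recurrences. Neither is in the documents. The range examined is k = 0 to 4 and m = 0 to 3, with each subject counted once.

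Formulas:
- cumulative = (k + m)/N
- new over all subjects = m/N
- new among those at risk = m/(N − k)
- intervals are exact (Clopper-Pearson) 95%

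*If the numerator is cumulative*, hold k + m = 3. The cumulative result is always 3/21 = 14.3% (3.0 to 36.3), but:

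| k known | m new | New among at risk | 95% CI |
|---|---|---|---|
| 0 | 3 | 3/21 = 14.3% | 3.0 to 36.3 |
| 1 | 2 | 2/20 = 10.0% | 1.2 to 31.7 |
| 2 | 1 | 1/19 = 5.3% | 0.1 to 26.0 |
| 3 | 0 | 0/18 = 0% | 0 to 18.5 |

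*If the numerator is new-only*, what remains is the denominator:

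| k known | m new | Over all 21 | Among at risk |
|---|---|---|---|
| 0 | 2 | 2/21 = 9.5% | 2/21 = 9.5% |
| 1 | 2 | 2/21 = 9.5% | 2/20 = 10.0% |
| 4 | 2 | 2/21 = 9.5% | 2/17 = 11.8% |
| 4 | 3 | 3/21 = 14.3% | 3/17 = 17.6% |

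With k = 0 all versions agree.

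**The case against.** **Pooling is not established.** The route through SAP 9.3 and Protocol 6.1.2 yields new events only. This stands. If the window is settled that way, the ambiguity between early and new failures disappears and only the label and the denominator need attention. The point therefore depends in part on the questionnaire window.

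**Cumulative recurrence is a legitimate long-term measure.** This stands too. The synopsis speaks of additional data to confirm performance over the longer term, which a cumulative figure can serve. A new-event proportion alone would drop early failures: in the last row of the first table, three failures in 21 would appear as 0/18. The cumulative figure must stay.

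**The split is partly recoverable.** With about 21 subjects, by-subject listings and the recurrence dates needed for the Kaplan-Meier curve, a reader who also held the T-GENVIH-002 results could probably separate early from new events. That eases the problem but does not replace a pre-specified summary.

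**No decision depends on it.** The study is descriptive, with no test or success criterion (Protocol 10.1, SAP 9.1), so no formal conclusion can flip. This limits the consequence to how the result is read.

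**A stronger reading to avoid.** Early outcomes existed before this study was written, so a reader might infer that the minimally invasive sub-population was taken forward because its early recurrence looked favourable. The documents do not support this. Protocol 2.3 and 4.2 give the rationale as adding data on minimally invasive cases, and Protocol 6.1.1 calls for the full consecutive series of them.

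**Conclusion.** The point holds in limited form. The objective is tied to unreported, later data; the primary summary is a single proportion; and no specified output estimates new recurrences among subjects still at risk. Whether that proportion mixes known with new events is an unresolved conflict in the documents, with the cumulative reading better supported.

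Under that reading, an assumed 3 recurrences in 21 gives 14.3% whether the new-event result is 0% or 14.3%. Under the new-only reading, the denominator effect is small for plausible counts: 0.5 percentage points with 1 early and 2 new, and 3.3 points (17.6% against 14.3%) with 4 early and 3 new. All event counts are assumptions, and the real size cannot be known because the documents do not give the number of earlier recurrences. If there were none, the estimates coincide.

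It would go too far to say that new recurrence among those at risk is the only valid measure of continued performance. It should be corrected before analysis, because the change is cheap and avoids choosing between figures after the results are seen.

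**What to change.** 1. Settle the event window: reconcile Protocol 6.1.2 and SAP 9.3 with the Protocol synopsis and SAP 5, and make the endpoint label match.
2. In SAP 9.3.1 and Protocol 10.4.3, report side by side, each with its own denominator and exact 95% CI:
   - (a) clinically confirmed recurrences already reported in T-GENVIH-002;
   - (b) new clinically confirmed recurrences among subjects recurrence-free at their last T-GENVIH-002 contact;
   - (c) cumulative clinically confirmed recurrence since the index repair.
3. State that conclusions about the period after T-GENVIH-002 rest on (b), and conclusions about overall long-term recurrence on (c).

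Cost: wording in two sections, reconciliation of the window text and two extra table rows. Earlier recurrence status should already be held, since the endpoint refers to what T-GENVIH-002 reported and SAP 9.2.2 to 9.2.4 already draw on that study's data. The downside is a slightly smaller denominator and wider interval for (b).

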10.4 Statistical Analyses

10.4.1 General Approach

Descriptive statistics will be used to summarize study outcomes. For categorical data, frequency counts and percentages will be provided. For continuous data, descriptive statistics, including sample size, mean, median, standard deviation, and range of values (i.e., minimum and maximum values) will be provided.

All data collected in this study will be provided in subject data listings. Data collected in this study will be reported using summary tables and graphs as appropriate to the data. Descriptive summary statistics (n, mean, median, standard deviation, minimum and maximum) will be calculated for the continuous variables and/or frequencies and percentages will be produced for the categorical variables.

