10.4.4 Analysis of the Secondary Endpoint(s)

Descriptive statistics will be provided for the following secondary endpoints:

1. Incidence of self-reported recurrence (i.e., bulge) of the primary hernia to date, including not previously reported in T-GENVIH-003 study.
2. Incidence of Surgical Site Occurrences requiring Procedural Intervention (SSOPI) of the primary hernia repair to date, including not previously reported in T-GENVIH-002.
3. Incidence of Surgical Site Occurrences (SSOs) of the primary hernia repair to date (seroma, abscess, dehiscence, hematoma, wound necrosis, ileus, fistula, delayed wound healing), including not previously reported in T-GENVIH-002 study.
4. Incidence of Surgical Site Infections (SSIs) post primary hernia repair to date, including not previously reported in GENVIH-002 study.
5. Incidence of reoperation requirement of the primary hernia repair to date, including not previously reported in GENVIH-002 study.

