9. STATISTICAL ANALYSES

9.1 General Statistical Considerations

Descriptive statistics will be used to summarize study outcomes. No formal statistical testing will be performed. The study objectives will be presented by summary statistics.

For categorical data, frequencies and percentages will be provided. For continuous data, descriptive statistics, including sample size, mean, median, standard deviation, and range of values (i.e., minimum, and maximum values) will be provided.

A separate Table Listing Graphs (TLFs) will be provided.

All statistical analysis will be conducted using SAS® for Windows, version 9.4 or later.

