9.2.8 Time to Hernia Recurrence Survival Analyses

Time to recurrence Kaplan-Meier Curve will be provided for all subjects with hernia recurrences at follow-up visits.

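### The SAP gives no confidence interval for the primary and secondary proportions in about 21 subjects, although the objectives speak of confirming or demonstrating performance

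*SAP*

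**What the plan says.** **Analysis.** SAP 9.3.1 closes its account of the primary endpoint with "The proportion of subjects with the incidents will be presented", and SAP 9.3.2 repeats the sentence for the five secondary endpoints. The general rule in SAP 9.1 is "For categorical data, frequencies and percentages will be provided". Protocol 10.4.1 has the same rule: "For categorical data, frequency counts and percentages will be provided". Protocol 10.4.3 adds only that "The primary endpoint for this study is descriptive statistics of clinically confirmed recurrence of the primary hernia to date", and Protocol 10.4.4 that "Descriptive statistics will be provided for the following secondary endpoints". SAP 9.2.8 plans a time-to-recurrence curve: "Time to recurrence Kaplan-Meier Curve will be provided for all subjects with hernia recurrences at follow-up visits". It names no confidence band.

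**Design.** Protocol 10.2 and SAP 8 both plan about 21 treated subjects. SAP 8 says this number does not come from hypothesis testing. Protocol 10.1 disclaims a formal hypothesis, and SAP 9.1 states "No formal statistical testing will be performed". On population, SAP 7 says "The endpoints analysis will be based on the Intent-To-Treat population". SAP 11 expects missing data and rules out imputation.

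**Objectives.** Seven statements use *confirm* or *demonstrate* about performance: the synopsis twice (study description and primary objective), Protocol 2.3 once, Protocol 3.1 twice, Protocol 10.1 once and SAP 3 once. Protocol 3.1 goes furthest, saying that the investigation will confirm safety as well as performance.

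**The concern.** The stated aim and the planned output do not match. To confirm or demonstrate something, one needs either a criterion the result could fail, or at least a view of how far the estimate might be from the truth. The plan has neither. No performance goal or success rule appears; the 31.8% recurrence rate in Protocol 2.1 is background on other materials and is not adopted as a target.

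With about 21 subjects, chance variation is large. A recurrence rate of 0% or 4.8% (1 of 21) looks reassuring, and Protocol 11.4 sends the final report to regulatory authorities. If the plan is followed as written, that report need not show that the same data are compatible with a much higher rate. The stake is how the result is read, not whether the counts are right.

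**Working it through.** **Inputs.** n = 21 comes from Protocol 10.2 and SAP 8. The documents give no expected event rate, response rate, confidence level or precision target. The sample size therefore cannot be reproduced, and need not be: it is the number expected from the laparoscopic and robotic subgroup of the earlier study. The event counts, the 95% level and the smaller values of n below are my assumptions.

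**Formula.** The exact (Clopper-Pearson) two-sided 95% limits for x events in n subjects are

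- lower = 0.025 quantile of Beta(x, n − x + 1), or 0 when x = 0;
- upper = 0.975 quantile of Beta(x + 1, n − x).

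For x = 0 the upper limit reduces to 1 − 0.025^(1/n). At n = 21 this is 1 − 0.025^(1/21) = 1 − 0.8389 = 0.161.

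**Results at n = 21.**

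| Events | Proportion | Exact 95% limits |
|---|---|---|
| 0 | 0% | 0 to 16.1% |
| 1 | 4.8% | 0.1 to 23.8% |
| 2 | 9.5% | 1.2 to 30.4% |
| 3 | 14.3% | 3.0 to 36.3% |

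The Wilson upper limit for 0 of 21 is 15.5%, so the message does not depend on the choice of interval.

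**The same point from the other side.** If the true rate were 5%, the chance of seeing no events in 21 subjects would be 0.95^21 = 0.34. If it were 10%, it would be 0.90^21 = 0.11.

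**Fewer subjects assessed (assumed).** Upper 95% limits:

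| Subjects assessed | 0 events | 1 event |
|---|---|---|
| 18 | 18.5% | 27.3% |
| 15 | 21.8% | 31.9% |
| 12 | 26.5% | 38.5% |

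**Which subjects form n.** SAP 7 requires receipt of the study intervention for the intent-to-treat population, and the protocol synopsis describes that intervention as the interview. On that reading, a subject never interviewed is outside the population altogether. A smaller n would then usually mean a smaller population, with less of it due to missing answers inside the population.

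**Which events count.** Most endpoints are worded as cumulative to date, including events not reported before. Surgical site occurrences requiring procedural intervention (SSOPI) are the exception. SAP 3.2 and Protocol 3.4 limit them to events not previously reported, while the synopsis and Protocol 10.1 and 10.4.4 use the cumulative wording. For a cumulative endpoint, an event recorded in T-GENVIH-002 is already known and needs no imputation. SAP 9.3, however, bases the endpoint analysis on the Visit 1 questionnaire, so the SAP should state the numerator for each endpoint.

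**The case against.** The strongest reply is that the study is openly descriptive. It has no hypothesis, no test and no decision rule, so no planned number becomes wrong. Counts accompany the percentages (SAP 9.1), SAP 9.2.6 adds by-subject listings for every primary and secondary endpoint, and SAP 9.2.1 tabulates disposition. A reader would see the small numbers and could work out the limits. The verbs in the objectives drive no analysis. Non-response and unequal follow-up may matter more than chance, and a binomial interval covers neither. For a complete consecutive series, an interval also needs the idea of a wider population of similar patients.

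Much of this stands. It makes the point an improvement in reporting and not a correction of an error, and the wording change is secondary. It does not remove the gap: an interval is estimation, fits a plan without tests, and belongs beside any statement about performance. Its limits can be stated in one sentence.

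Three stronger readings are tempting, and the documents do not support them:

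- *The report would give a bare percentage.* It would not; counts and listings are planned.
- *About 21 subjects is too few, so the sample size is wrong.* No hypothesis or precision target is set against which it could fail.
- *A subject with no answer can never be counted as an event.* This is too absolute, because a recurrence already recorded in T-GENVIH-002 may count under the cumulative wording.

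Nor does either document plan an explicit conclusion of confirmed performance drawn from a percentage. That is a risk raised by the wording of the objectives, not a planned step.

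**Conclusion.** The point holds as a cheap improvement that should be made. Neither text plans a measure of precision for the primary or secondary proportions, while seven statements speak of confirming or demonstrating performance and no criterion is given. With 21 subjects assessed, even zero recurrences leaves a true rate of up to 16.1% compatible with the data; three recurrences leave a range of 3.0 to 36.3%.

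These limits assume that the 21 behave like a random sample of similar patients, each with a known status. They describe chance alone. Bias from subjects not reached and from differing lengths of follow-up is outside them. The finding concerns the SAP and protocol text only, since the separate output shells were not available.

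**What to change.** **SAP 9.3.1 and 9.3.2.** Add:

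> Each primary and secondary proportion will be shown as x/n (%) with an exact (Clopper-Pearson) two-sided 95% CI, where n is the number of ITT subjects whose status for that endpoint is known; the number with unknown status will be shown. The interval is descriptive, treats the series as a sample of similar patients, and does not cover bias from subjects not reached or differing follow-up.

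State for each endpoint whether events recorded in T-GENVIH-002 count, and settle the SSOPI wording. Where the endpoint is cumulative, treat such an event as known. Report subjects who were not interviewed, and may therefore fall outside the ITT population, in the disposition table of SAP 9.2.1.

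**SAP 8.** Add:

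> With 21 subjects assessed, the exact two-sided 95% CI is 0 to 16.1% for 0 events, 0.1 to 23.8% for 1, 1.2 to 30.4% for 2 and 3.0 to 36.3% for 3.

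**SAP 3.** Replace *demonstrate* with *describe* or *estimate*. Align the six protocol statements at the next amendment, if there is one; the interval need not wait for it. With descriptive wording, no benchmark is required.

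**Cost.** A few sentences in the SAP and a small change to the output programs. The price is a more modest stated conclusion.

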1.1 Protocol Synopsis

Title	A Prospective Analysis of the Use of GENTRIX® Surgical Matrix for Soft Tissue Reinforcement in Ventral Hernia Repair as Long Term Follow Up (LTFU) to T-GENVIH-002 study
Short Title	GENTRIX Ventral Hernia Repair LTFU study
Protocol Number	T-GENVIH-003
Study Description	The purpose of this study is to collect additional safety data and demonstrate the performance of Integra GENTRIX® Surgical Matrix for reinforcement of ventral hernia repairs from a sub-population of participants in the T-GENVIH-002 study, specifically those with laparoscopic or robotic repair. Prospective data will be collected and assessed for later post-operative surgical site events and complications in the post-operative period from the last timepoint of data collection in T-GENVIH-002 to present.
Pre/Post-Market	Post-Market
Product(s)	GENTRIX® Surgical Matrix - (6-layer), - Plus (8-layer), and -Thick *Refer to APPENDIX I at the end of the protocol for product-specific Stock Keeping Units (SKUs) to be included in this study.
Indications for Use	GENTRIX® Surgical Matrix is intended for implantation to reinforce soft tissue where weakness exists in patients requiring gastroenterological or plastic & reconstructive surgery. Reinforcement of soft tissue within gastroenterological and plastic & reconstructive surgery includes, but is not limited to, the following open or laparoscopic procedures: hernia (e.g., hiatal/ diaphragmatic) and body wall repair, colon and rectal prolapse repair, tissue repair, and esophageal repair. GENTRIX® Surgical Matrix minimizes tissue attachment to the device in case of direct contact with viscera.
Study Design	Single-Arm, Prospective, Single-Center
Study Rationale	This study adds to the available data evaluating the safety and effectiveness of GENTRIX® Surgical Matrix in ventral hernia repair, particularly in a real-world population and particularly in the sub-

	population of minimally invasive surgery (MIS) cases (i.e., laparoscopic and robotic) from the GENVIH-002 study.
Primary Objective	The primary objective of this study is to capture additional existing clinical performance data to confirm the continued performance of the Gentrix® Surgical Matrix over longer term.

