2.1 Background

Ventral hernias are a type of abdominal hernias that can occur at any location along the vertical abdominal wall. Typically, these defects are acquired resulting from complications of a prior surgery, trauma, or natively weak points of the abdominal wall in some individuals. Obesity may contribute in large part to the weak points due to cyclic patterns of weight gain and loss. One in eight patients will develop an incisional hernia after abdominal surgery¹.

Ventral hernia repair is one of the most common surgical procedures performed in the United States. Every year there are approximately 350,000 repairs performed in the US with an estimated cost of \$3.2 billion.² Different patient populations require different solutions in order to make a repair as cost-effective and risk-averse as possible.

Clinical evidence has shown that primary suture repair of a ventral hernia alone results in high recurrence rates (>50%), and that all incisional hernia repairs should be reinforced with surgical mesh.^{3,4} Despite this consensus, due to the large variety of surgical meshes available currently, there is a lack of consensus on the ideal material for each repair. Ventral hernia treatment decisions are typically tied to patient operative risk, symptomatic concerns, and potential clinical complications of the repair.

Permanent synthetic mesh has been the standard of care in the reinforcement of simple, clean hernias due to its minimal cost and history of low recurrence.^{5,6} However, due to the inherent permanence, long-term complications such as product migration, contraction, erosion, and infection are common.⁵⁻⁸ In the complex hernia setting, synthetic materials may not be ideal due to the increased risks of surgical site occurrences (SSOs) and resulting recurrences.⁵⁻⁸ These complications can prove costly with each hernia recurrence and wound event estimated to cost an additional \$44,000 and \$85,000 respectively.^{9,10} Specifically, a mesh infection can cost up to \$140,000 and may require explantation of the mesh altogether.¹⁰

Biologically-derived materials, such as acellular dermal matrices, were developed for use in complex hernia repair to mitigate some of the risks seen with synthetic materials. However, long-term study of these materials demonstrated a 31.8% recurrence rate and 36.6% wound infection rate at 18.2 months follow-up.¹¹

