3.3 Primary Endpoint

The primary endpoint of this prospective study is to determine the incidence of clinically confirmed recurrence of the primary hernia to date, including not previously reported in T-GENVIH-002 study.

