6.1.2 Visit 1 Questionnaire

The patients' data to be collected from the last data collection of GENVIH-002 study to date, including not previously reported, are:

- Clinically confirmed recurrence of the primary hernia repair
- Self-reported recurrence (i.e., bulge) of the primary hernia
- Surgical Site Occurrences requiring Procedural Intervention (SSOPI)
- Surgical Site Occurrences (SSOs)
- Surgical Site Infections (SSIs)

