10.1 Statistical Hypotheses

This is a prospective, single-arm, single center post-market study to capture existing clinical performance data to confirm the continued performance of the GENTRIX® Surgical Matrix. A formal hypothesis does not apply to this study. Subjects from that consecutive series will be included in the study based on the defined inclusion and exclusion criteria.

T-GENVIH-003 study

Confidential

Protocol Version: V1.0 dated 02AUG2023

Page 35 of 41

This document contains proprietary and confidential information of Integra LifeSciences Corporation. Integra's confidential information may not be used, disclosed or reproduced without the prior written consent of Integra LifeSciences Corporation.

Primary Endpoint(s):

The primary endpoint of this prospective study is to determine the incidence of clinically confirmed recurrence of the primary hernia to date, including not previously reported in T-GENVIH-002 study.

Secondary Endpoint(s):

1. Incidence of self-reported recurrence (i.e., bulge) of the primary hernia to date, including not previously reported in T-GENVIH-003 study.
2. Incidence of Surgical Site Occurrences requiring Procedural Intervention (SSOPI) of the primary hernia repair to date, including not previously reported in T-GENVIH-002.
3. Incidence of Surgical Site Occurrences (SSOs) of the primary hernia repair to date (seroma, abscess, dehiscence, hematoma, wound necrosis, ileus, fistula, delayed wound healing), including not previously reported in T-GENVIH-002 study.
4. Incidence of Surgical Site Infections (SSIs) post primary hernia repair to date, including not previously reported in GENVIH-002 study.
5. Incidence of reoperation requirement of the primary hernia repair to date, including not previously reported in GENVIH-002 study.

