8. SAMPLE SIZE DETERMINATION

Subjects from that consecutive series will be included in the study based on the defined inclusion and exclusion criteria, the subgroup of T-GENVIH-002 subjects underwent Laparoscopic or Robotic surgery. The sample size is not based on hypothesis testing. The planned sample size for this study will be approximately 21 treated subjects.

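### The primary recurrence result is a proportion with no time since repair attached, so by itself it does not show longer-term performance

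*SAP*

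**What the plan says.** The Protocol Synopsis (1.1) gives the primary objective as being to "confirm the continued performance of the Gentrix® Surgical Matrix over longer term". The primary endpoint in Protocol 3.3 is the "incidence of clinically confirmed recurrence of the primary hernia to date", with no fixed horizon. SAP 3.1 defines it the same way. For its analysis, SAP 9.3.1 says only: "The proportion of subjects with the incidents will be presented".

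The planned summaries in SAP 9.2 cover disposition, demographics, history, medication, the Visit 1 items, study exit, a recurrence curve and complications. None is a summary of time since repair. Surgery evaluation (9.2.5) is marked not applicable. The Visit 1 list in Protocol 6.1.2 includes "Clinically confirmed recurrence of the primary hernia repair" but names no date of recurrence and no date last known free of it.

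SAP 9.2.8 does plan a time-to-recurrence Kaplan-Meier curve, for the subjects who had a recurrence. It states no time origin, censoring rule, reporting time or number at risk.

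The start of the observation window differs between places. It is the day of surgery in the Synopsis row on study visits and in SAP 5. It is the last T-GENVIH-002 data collection in the Synopsis study description, Protocol 6.1.2 and SAP 3.

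**The concern.** Recurrence accumulates with time, so a cumulative percentage has meaning only with the time over which it built up. Subjects come from a consecutive surgical series (Protocol 6.1.1) and are all interviewed within a study of about 3 months (Protocol 5.4). Time since repair is therefore set by when each operation took place, and the planned output does not report it.

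A reader of the final report could not tell a low recurrence rate over many years from a higher rate over a short period. That distinction is the purpose of a long-term follow-up study. The two window definitions add to the difficulty: it is unclear whether the proportion counts all recurrences since surgery or only those since the earlier study ended.

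**Working it through.** **The plan's own figure.** There is no calculation to reproduce. SAP 8 says: "The planned sample size for this study will be approximately 21 treated subjects". It also says: "The sample size is not based on hypothesis testing". The number is the size of an available subgroup, and no error in it is claimed.

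**Inputs.** N = 21 (SAP 8). Repair dates, follow-up lengths and this device's recurrence rate are not in the documents. I assume constant hazards h of 3%, 5% and 10% per year, with follow-up spread evenly from a to b years.

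**Effect of follow-up length.** The expected crude proportion is the average of 1 − exp(−ht) over a to b, which is

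1 − [exp(−ha) − exp(−hb)] / [h(b − a)].

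For h = 0.05:
- 1 to 3 years: 1 − (0.9512 − 0.8607)/0.10 = 9.5%
- 2 to 6 years: 1 − (0.9048 − 0.7408)/0.20 = 18.0%
- 6 to 8 years: 1 − (0.7408 − 0.6703)/0.10 = 29.5%

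| Follow-up | 3%/year | 5%/year | 10%/year |
|---|---|---|---|
| 1 to 3 years | 5.8% | 9.5% | 18.0% |
| 2 to 6 years | 11.3% | 18.0% | 32.5% |
| all at 4 years | 11.3% | 18.1% | 33.0% |
| 6 to 8 years | 18.9% | 29.5% | 50.3% |

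At any one hazard, length alone moves the result about threefold (29.5/9.5 = 3.1). Read across the table, a result of 18% fits 10% per year over 1 to 3 years as well as 5% per year over 2 to 6 years.

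**Effect of unequal follow-up.** Compare 2 to 6 years with everyone at 4 years, which has the same mean: 18.0% against 18.1% at 5% per year, and 32.5% against 33.0% at 10%. Spread around a given mean hardly matters here.

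**Whether SAP 9.2.8 supplies the estimate.** Take invented data: recurrences at 1, 2.5 and 4 years, and 18 subjects censored evenly from 2 to 6 years.
- Crude proportion: 3/21 = 14.3% (exact 95% CI 3.0% to 36.3%).
- Kaplan-Meier over all 21, with 21, 17 and 10 at risk at the three events: 1 − (20/21)(16/17)(9/10) = 19.3% at 4 years.
- Kaplan-Meier over the three recurrences only, as 9.2.8 is worded: 1 − (2/3)(1/2)(0/1) = 100% at 4 years, whatever happened to the other 18.

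The last curve describes when recurrences happened among those who had one. It does not estimate the risk of recurrence.

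**The case against.** The study is small and descriptive. Protocol 10.1 says: "A formal hypothesis does not apply to this study". Time is not ignored either. A Kaplan-Meier curve cannot be drawn without dates, and the wording of 9.2.8 may be loose drafting for a curve over everyone. Protocol 7.2.4 lists recurrence of the tissue defect as an anticipated adverse event, Protocol 7.3.1 asks for onset dates, and SAP 9.3.4 lists them. SAP 9.2.2 to 9.2.4 already draw on T-GENVIH-002 data, so surgery dates can probably be obtained. Protocol 10.4.2 speaks of patients who completed the earlier study, which implies some minimum follow-up.

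Much of this stands, and it rules out several stronger readings.
- A reader might infer that the questionnaire asks whether a recurrence occurred but not when. The form itself is not in the documents, and the sections above imply that some dates are captured.
- A reader might infer that unequal follow-up is the main distortion. The 18.0% against 18.1% comparison says otherwise.
- A reader might set the result against the background figure of "31.8% recurrence rate and 36.6% wound infection rate at 18.2 months follow-up". That figure concerns acellular dermal matrices in complex hernia, and neither document plans a comparison with it.
- A reader might infer that a low result would only reflect recent repairs. Repair dates are not given, so this is unknown.

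The objection does not remove the omission. A descriptive incidence still needs its observation period, and being able to derive follow-up is not a plan to report it. Even if 9.2.8 were read as covering all subjects, it would still lack an origin, a censoring rule and reporting times.

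**Conclusion.** The point holds for the primary result as specified. Followed exactly, SAP 9.3.1 yields a percentage tied to no time after surgery, and that percentage does not by itself show performance over the longer term. It would be too strong to say that the study as a whole cannot do so. With follow-up reported and a Kaplan-Meier estimate over all subjects, it could, within the limits of its size.

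The main fault is the unreported length of follow-up: about a threefold range at a given hazard, from 9.5% to 29.5% at 5% per year. This rests on assumed constant hazards and assumed follow-up ranges. That repair times vary is an inference from a consecutive series interviewed over about 3 months.

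The wide confidence interval at 21 subjects is a separate limit. It does not excuse the omission, because an interval around a proportion without a time is no easier to interpret. This is a cheap change that should be made.

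**What to change.** Keep the proportion. In SAP 9.3.1 add:
1. Median, quartiles and range of time from the index repair (T-GENVIH-002 surgery date) to last known recurrence status.
2. A Kaplan-Meier estimate of cumulative recurrence over all analysed subjects, with origin at the index repair and censoring at the date last known recurrence-free. Report it at prespecified times with 95% confidence intervals and numbers at risk. Choose the times from the surgery dates before outcomes are seen, and align 9.2.8 with this.

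In Protocol 6.1.2, make sure the Visit 1 form records the month and year of recurrence diagnosis and the date last known recurrence-free. State whether a telephone interview without an examination counts for the latter.

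Reconcile the start of the window: day of surgery (Synopsis study visits row, SAP 5) or last T-GENVIH-002 collection (Synopsis study description, Protocol 6.1.2, SAP 3).

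The cost is up to two date fields and a few lines of the SAP. Recalled dates will be approximate, so month and year precision has to be accepted. Estimates from about 21 subjects will be imprecise, which is why the intervals and numbers at risk are needed.
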